### 6.2.3 Allocation to Interventional Group

Subjects who meet eligibility criteria and complete their baseline assessment visit will be randomly assigned to the intervention or waitlist condition. We will use a permuted randomized block design that randomly mixes blocks of different sizes (2 to 6) to assign 40 eligible participants to CBT or waitlist conditions using a one-to-one allocation ratio. This randomization design was selected due to the need to create exactly the same group sizes with a small sample. A statistician will conduct the randomization using a computer-generated algorithm.

## 7 Study Interventions

**CBT Intervention.** The CBT intervention (Table 1) will consist of weekly, 50-minute individual meetings for 16 weeks with a clinician trained in CBT for binge eating disorder. The treatment will be administered using a manualized treatment protocol adapted from Fairburn and Mitchell. The overall goals of CBT for BED are to interrupt binge-eating behavior, learn self-management strategies to help reinstitute more normal eating habits, change erroneous beliefs about weight and shape and develop healthier attitudes towards one's body. Participants are taught a variety of skills including identifying triggers of binge eating episodes, correcting beliefs or thought patterns related to binge eating, and altering attitudes regarding food and eating. Homework is assigned at each session so participants can practice the skills that they have learned. To monitor treatment integrity and adherence, treatment sessions will be reviewed under the supervision of Drs. [name] or [name]. This treatment has been tested in a number of trials for BED and we anticipate seeing 50% of individuals with full remission from binge eating and a 68-90% reduction in the number of binge eating episodes.

Table 1. CBT for BED Intervention

Stage	Aim	Weeks
1: Introduction	Jointly creating a formulation of the processes maintaining the eating disorder Establish real-time monitoring of eating and other relevant thoughts and behavior Provide education about body weight regulation and fluctuations, the physical complications and the adverse effects of dieting Introduce weekly weighing Introduce a pattern of regular eating	1-4
2: Transition	Jointly reviewing progress Identify barriers to change Modify the formulation as needed	5-6

	Plan Stage Three	
3: Main body of treatment	Address key mechanisms that are maintaining BED Overevaluation of shape and weight - Provide education about overevaluation and its consequences - Reduce unhelpful body checking and avoidance - Relabel unhelpful thoughts or feelings such as “feeling fat” - Develop previously marginalized domains of self-evaluation - Explore the origins of the overevaluation Dietary restraint - Change inflexible dietary rules into flexible guidelines - Introduce previously avoided food Event triggered changes in eating - Develop problem-solving skills to directly tackle such events - Develop skills to accept and modulate intense moods	7-14
4: Final stage	Provide education about realistic expectations Devise a short-term plan for the months following treatment Devise a long-term plan to minimize relapse in the future	15-16

**Waitlist Control Group.** Participants who are assigned to the wait-list group will complete their assessment visits at baseline and 16 weeks. We will request that they not seek treatment for weight or binge eating disorder during the wait period. This will be verified at a brief telephone call check-in at week 8 where we will also update the patient on their study status, as well as at the week 16 visit. After they complete their post-treatment assessment, they will be offered the 16-week cognitive behavioral therapy treatment. At their last treatment session, they will be asked to complete a brief assessment on the effect of the CBT treatment.

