## 1. BACKGROUND AND STUDY RATIONALE

### 1 Background and Relevant Literature

**Binge Eating Disorder (BED).** BED is a serious public health problem. It is characterized by eating, in a discrete period of time, an amount of food that is larger than most people would consume under similar circumstances. Patients report a sense of loss of control over eating, followed by distress about their behavior. The prevalence of BED is 2.8% among US adults. BED affects twice as many females as males but is comparable in prevalence across racial/ethnic groups. BED has a chronic course and leads to progressive weight gain if left untreated. BED and obesity are highly comorbid, and the frequency of binge eating episodes is strongly associated with body mass index (BMI). Individuals with BED have a higher prevalence of medical and psychiatric morbidities compared to individuals without BED, including metabolic syndrome, functional impairment, and lower quality of life. Patients with BED differ behaviorally, psychologically, genetically, and physiologically from persons with other forms of obesity and eating disorders; notably, these individuals have high levels of dietary disinhibition and food reward sensitivity. BED represents a vulnerable phenotype of obesity for which there is an urgent need for better treatment approaches.

**Critical Need for Better BED Treatment Approaches.** Treatment options for BED remain limited and are often not sufficient for patients. Current available treatments include psychotherapy, behavioral weight loss, and pharmacotherapy. A specific type of psychotherapy, cognitive behavioral therapy (CBT), is the most effective treatment for BED. CBT is associated with significantly higher binge eating abstinence rates than no treatment and abstinence rates are 15-44% higher in CBT than behavioral weight loss. Unfortunately, even with CBT, roughly half of patients with BED do not achieve full remission of binge eating, and there are no reliable predictors of treatment response. Further knowledge is needed about how to best prevent and treat BED. Effective prevention and treatment strategies rely on a better understanding of both the etiology and maintenance of binge eating behaviors.

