### 5.3 Exclusion Criteria

1. Weight > 158.8 kg (350 lbs, due to scanner weight restrictions)
2. Supine abdominal width (with arms folded above) > 70 cm or sagittal diameter > 50 cm (due to scanner dimension restrictions)
3. Pregnant or nursing (or plans to become pregnant in the next 5 months)
4. Evidence of psychiatric disorder that significantly interferes with daily living
5. Active suicidal ideation
6. Self-reported type 1 diabetes or type 2 diabetes
7. Use of weight loss medications or other agents known to affect body weight (e.g., oral glucocorticoids, second-generation antipsychotic medications) in the past 3 months
8. Psychiatric hospitalization within the past 6 months
9. Self-reported alcohol or substance abuse within the past 12 months, including at-risk drinking (current consumption of  $\geq 14$  alcoholic drinks per week)
10. Self-reported use of illicit drugs within the past 30 days
11. Presence or history of orthopedic circumstances, metallic inserts, pacemaker, claustrophobia, or other conditions that may interfere with magnetic resonance imaging
12. Loss of  $\geq 10$  lb of body weight within the past 3 months
13. History of (or plans for) bariatric surgery
14. Visual, auditory, or other impairment that would affect task performance
15. Epilepsy or other brain injury
16. Participation in individual psychotherapy for BED in the prior 3 months
17. Inability to attend treatment and lack of capacity to provide informed consent
18. Any serious or unstable medical or psychological condition that, in the opinion of the investigator, would compromise the patient's safety or successful participation in the study

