## 6 Procedures

### 6.1 Recruitment, accrual, and retention.

We will recruit participants at a single site – the Center for Weight and Eating Disorders at the University of Pennsylvania, Philadelphia, PA, USA - through local media advertisements and news shows/outlets, as well as Internet-based advertising outlets and flyers and brochures around our community. We also will advertise using clinician referrals from primary care clinics affiliated with the University of Pennsylvania Health System. We will be recruiting from the university-based website, iConnect, which allows access to their volunteer registry data of potential participants. We will use study condition terms such as “binge eat\*”; “eating disorder\*”; and/or obesity. Recruitment may also use Penn media services (e.g., communications) and social media (e.g., Facebook, Twitter; please see attached for information about Facebook recruitment). We conservatively estimate a drop-out rate of 25% based on prior experience in our labs and will enroll 40 participants to have 30 complete the study. Based on prior studies of BED in our labs, we expect to screen 50 to 75 females who respond to our advertisements per month and enroll about 5 females each month. To minimize attrition we will use multiple evidence-based strategies that improve retention rates including scheduling sessions at convenient times, maintaining close contact, and providing compensation for assessment visits and travel costs. Travel compensation will be given at the end of each CBT session, as applicable. Our research group has successfully completed a number of long-term intervention and fMRI trials that have lasted >4 months with attrition rates <20%.

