## **8 Statistical Plan**

### **8.1 Sample Size and Power Determination**

The power calculation is based on current standards in exploratory neuroimaging studies. Previous fMRI studies that used groups of 15 subjects per condition were sufficient to detect significant differences in BOLD signal response to behavioral tasks. Due to resource limitations, our sample size will be limited. The sample size will allow us to detect effect sizes of 0.93 or larger in BOLD signal between groups with 80% power controlling for type 1 errors at 5% using a one-sided test.

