### Potential Study Risks

#### Risks of Assessments, CBT Treatment, and Waitlist

Occasionally a person suffering from BED may find answering questions about their illness distressing. Some of the questions in the interview that assess history of psychological conditions may be of a personal nature. Additionally, some of the topics discussed and audio recorded during cognitive behavioral therapy will be sensitive and may induce emotional responses or discomfort for some participants. All such questions will be asked by trained clinicians and a licensed clinical psychologist will be available at all times to consult with the participant should this occur. Appropriate referrals will be given as necessary.

Participants in the waitlist group will be contacted at week 8 via phone by a research assistant to keep participants engaged and enhance study retention. All waitlist participants will be provided with the 16-week CBT intervention after they complete the end-of-study testing at

week 16. Though we considered other designs, a waitlist control comparison was selected as it was deemed ethical, while also permitting a non-intervention comparison and maximizing power to detect differences between groups. Patients seeking treatment for BED in the community are often on waitlists for more than 4 months due to the lack of skilled clinicians available. For the majority of participants, the waitlist will still be shorter than routine services. Attrition is no worse with waitlist control groups than with active BED treatment.

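### Outside non-drug weight or BED treatment is discouraged and checked in the waitlist arm only, so the arms are handled unequally after randomization

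*Combined protocol and SAP*

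**What the plan says.** **What counts as treatment.** The background in section 1 states: "Current available treatments include psychotherapy, behavioral weight loss, and pharmacotherapy".

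**Entry.** Section 5.3, item 16, excludes "Participation in individual psychotherapy for BED in the prior 3 months". Other items exclude recent use of weight-loss drugs or other agents that affect body weight (item 7), a loss of 10 lb or more in the past 3 months (item 12), and past or planned bariatric surgery (item 13). No item names group therapy for BED or a behavioral weight-loss programme.

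**After randomization, waitlist arm.** Section 7, Waitlist Control Group: "We will request that they not seek treatment for weight or binge eating disorder during the wait period". Staff check this in a week 8 call and at the week 16 visit.

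**After randomization, CBT arm.** The CBT paragraph and Table 1 in section 7 describe the sessions, supervision and content. They contain no matching request and no question about outside treatment.

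**Recording.** Table 2 lists medications at screening and T2 and a review of medication changes at T2. The waitlist-only heading appears to cover just the second treatment period and T3, so these T2 rows apply to both arms. The adherence row covers sessions attended and skill-building work. No row covers non-drug co-treatment.

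**Purpose and analysis.** The risk section (section 19) justifies the waitlist as "permitting a non-intervention comparison and maximizing power to detect differences between groups". Section 8.3 plans an intention-to-treat primary analysis and further analyses of protocol-compliant participants. It does not define compliance, and section 8 does not say how outside treatment is handled.

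**The concern.** Aims 1 and 2 read the between-arm difference in neural change as the effect of CBT. Randomization balances what women bring to the trial. It does not balance what the protocol then causes to differ. A waitlist woman who thinks of joining a weight-loss group is asked not to and is questioned twice. A CBT woman who joins the same group is neither asked nor recorded. If co-treatment ends up more common in the CBT arm, its effect is added to the CBT estimate, and nothing in the CBT arm's data would show it.

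The second exposure is in section 8.3. Only waitlist women are under a rule about outside treatment and only they are asked about it. As written, they are the only ones who could be classed as non-compliant for non-drug outside treatment. The same behaviour in the CBT arm would stay in the analysis.

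**Working it through.** **1. The plan's own figure.** Section 8.1 states: "The sample size will allow us to detect effect sizes of 0.93 or larger in BOLD signal between groups with 80% power". The same section sets a one-sided 5% level. Section 6.1: the trial "will enroll 40 participants to have 30 complete the study", which is 15 per arm at 1:1 allocation (section 6.2.3). A two-sample t-test with 15 per arm at one-sided 5% has 79.95% power at 0.93 SD and a detectable effect of 0.931 SD. The stated figure is reproduced, and this point does not change it.

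**2. Coverage of the treatment types named in section 1.**

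| Treatment | Barred at entry | Follow-up, waitlist | Follow-up, CBT |
|---|---|---|---|
| Individual psychotherapy for BED | Yes, prior 3 months | Requested not to seek; checked weeks 8 and 16 | No request, not recorded |
| Group therapy for BED | No | As above | No request, not recorded |
| Behavioral weight-loss programme | Not as such; only if 10 lb or more already lost | As above | No request, not recorded |
| Drugs | Agents affecting weight, past 3 months | As above; medications recorded at T2 | No request; medications recorded at T2 |

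The asymmetry that leaves no record is in the non-drug rows.

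**3. When it biases the contrast.** Let p1 and p0 be the shares with outside treatment in the CBT and waitlist arms, and g its added effect in SD units, taken as additive. The shift in the CBT minus waitlist difference is (p1 − p0) × g.

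- Equal continuation, p1 = p0: the shift is 0.
- Unequal handling, p1 ≠ p0: the shift is not 0, and its sign depends on which share is larger.
- Equal shares p in both arms, but waitlist users removed from the protocol-compliant set while CBT users stay: the shift is p × g − 0 = p × g. Here the selective exclusion alone creates it. This assumes that the removed women do not differ in other ways.

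**4. Illustration only.** The documents give neither p nor g. Both are assumed, with 15 per arm, one-sided 5% and equal SDs.

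- 10% to 30% of the CBT arm only, g = 0.5 to 0.93: the shift runs from 0.10 × 0.5 = 0.05 SD to 0.30 × 0.93 = 0.28 SD. With no true CBT effect, the chance of a positive result rises from 5% to 6.5% at the low end and 18.4% at the high end.
- Opposite direction, 10% to 30% of the waitlist arm only, with treatment as effective as CBT: the effect becomes 0.93 × 0.90 = 0.84 SD to 0.93 × 0.70 = 0.65 SD, and power falls from 80% to 72% and 54%.

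For scale, the standard error of the difference is √(2/15) = 0.37 SD.

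**The case against.** The case on the other side is substantial, and much of it stands.

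- A reader might infer that entry bars only individual psychotherapy and weight-loss drugs. Section 5.3 also bars other weight-affecting agents, bariatric surgery and recent loss of 10 lb or more.
- A reader might infer that all co-treatment goes unrecorded. Table 2 records medications in both arms at T2, so the gap is non-drug treatment.
- A reader might infer that the no-treatment comparison is left unprotected. The waitlist is the arm with a request and two checks. The gap is on the CBT side.
- A reader might put a figure on the bias. Suppose 10% to 20% of each arm (2 to 4 of 20 women) enter in a programme with half the effect of CBT, waitlist women stop and CBT women continue. The overstatement is then 0.10 to 0.20 × 0.5 = 5% to 10% of the CBT effect. At 0.93 SD that is 0.05 to 0.09 SD, about 13% to 25% of one standard error. The inputs are not in the documents, and a request not to seek treatment does not clearly require anyone to leave a programme already under way. If such programmes continue in both arms, they roughly cancel. A programme running at entry may also be partly reflected in the baseline scan.
- Items in section 5.3 govern entry and section 7 governs waitlist conduct, so the two do not contradict each other. With balanced arms, a wider exclusion is not needed for an unbiased contrast.

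None of this answers the remaining point. The request and the checks are written for one arm, non-drug co-treatment in the other has no place in the record, and the protocol-compliant set is undefined.

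**Conclusion.** The concern holds in a limited form. Outside weight or BED treatment is handled differently by arm after randomization: the waitlist arm is asked and checked, while non-drug co-treatment in the CBT arm is neither restricted nor recorded. Women in group BED therapy or a behavioral weight-loss programme can enroll.

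The direction and size of any bias cannot be derived from the documents. The 0.05 to 0.28 SD range rests on assumed prevalence, assumed added effect, additivity and co-treatment confined to one arm. It shows what could matter with 15 completers per arm and is not an estimate. The documents do not support the stronger inference that the CBT effect will be overstated. They do support two statements: an imbalance of this kind could not be detected from the planned data, and the section 8.3 protocol-compliant analysis could, as written, remove only waitlist women for outside treatment. This is an inexpensive improvement to make, not a flaw that undermines the primary intention-to-treat comparison.

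**What to change.** 1. Put the same request and the same questions to both arms at week 8 and T2, covering any weight or BED treatment and naming non-drug treatment explicitly.
2. Record the answers in the CRF and add a row to Table 2.
3. Define protocol-compliant in section 8.3 with one co-treatment criterion, applied identically in both arms, before any outcome data are examined.
4. The sponsor should consider whether exclusion 16 should also cover group BED therapy and structured weight-loss programmes, in line with the treatments listed in section 1 and the scope of the waitlist request in section 7. This is an eligibility decision for the sponsor, and steps 1 to 3 do not depend on it.

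The cost is two short questions per participant; CBT participants are already seen weekly and waitlist participants are already contacted at week 8 and seen at week 16. If exclusion 16 is widened, a few screened women become ineligible, against the 50 to 75 screened and about 5 enrolled per month expected in section 6.1.

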### 7.1 Vulnerable Populations:

Children, pregnant women, fetuses, neonates, or prisoners are not included in this research study. Although not directly targeted, mentally disabled persons, economically or educationally disadvantaged persons, and/or employees or students of the University of Pennsylvania will not be denied enrollment and any special protections and/or additional safeguards will be undertaken in order to protect the rights and welfare of these subjects from coercion or undue influence as appropriate.

Table 2. Study Assessment Schedule

	Waitlist Group Only					
	Screen	T1	Intervention or Waitlist (16 weeks)	T2	Intervention (16 weeks)	T3
Informed Consent- General	X					
Informed Consent- Audiorecording BED Assessment	X			X		X
Informed Consent- Audiorecording treatment sessions	X		X		X	
Demographic and Clinical Variables						
Review inclusion/exclusion criteria	X					
Demographics	X					
Medical history and physical exam	X					
Prior/concomitant medications	X			X		X
Review medication changes and updates				X		X
Vital signs (BP, HR)	X					
Pregnancy test	X					
MINI	X					
Menstrual diary	X	X	X	X		
BMI	X	X	X	X		X
Profile of Mood States (Brief Form)		X		X		
Scales for stress, hunger, food cravings, fatigue		X		X		
Responses to Script-Driven Imagery Scale		X		X		
Outcome Measures						
fMRI scan (SST, Script-driven imagery)		X		X		
Eating Disorder Examination	X			X		X
Reward-Based Eating Drive Scale		X		X		
Three Factor Eating Questionnaire		X		X		
Additional Questionnaires (described in Section 6.2)		X		X		X
Intervention adherence/fidelity						
Sessions attended, skill builders completed			X			
Adverse event/unanticipated problems assessment		X	X	X		X

Note. T1=Baseline; T2=16 week follow-up. T3=Assessment of post-CBT treatment outcomes for the waitlist group only. SST=Stop signal task.

## 7.2 Subject Withdrawal

Subjects may withdraw from the study at any time without impact to their care. They may also be discontinued from the study at the discretion of the Investigator for lack of adherence to intervention or study procedures or visit schedules, AEs, or due to subject pregnancy or intention of becoming pregnant. The Investigator may also withdraw subjects who violate the study plan, or to protect the subject for reasons of safety or for administrative reasons. It will be documented whether or not each subject completes the clinical study.

*Lost to follow-up:* In the case of subjects who do not return to the Center for study procedures and cannot be contacted, study personnel will make vigorous and repeated attempts (minimum of 3) to contact the subject. These attempts will include at least 1 mailing. If all attempts to contact the subject fail, that subject will be considered to be lost to follow-up and discontinued from the study.

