### 6.2.2 Post-Treatment Visit (Waitlist Group Only)

After individuals in the WL group complete their second fMRI assessment, they will be offered CBT treatment. For Specific Aim 3, the WL group will be asked to complete a brief assessment after their last CBT session to measure treatment response (i.e., the number of BE episodes in the past 28 days).

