### **Subject Replacement**

Subjects who prematurely discontinue from the study or become ineligible will not be replaced once they have been randomized. Every effort will be made to obtain follow-up data on all participants randomized.

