### 8.3 Subject Population(s) for Analysis

We will use an intention-to-treat approach of all randomized participants for all primary analyses. Additional analyses will be conducted with protocol-compliant participants.

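### Section 7.2 allows discontinuation from the study for poor adherence to CBT, and nothing assures week-16 data from those participants for the intention-to-treat analysis

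*Combined protocol and SAP*

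**What the plan says.** Section 7.2 (Subject Withdrawal) allows a participant to be "discontinued from the study at the discretion of the Investigator for lack of adherence to intervention or study procedures or visit schedules". It adds a further discretionary ground: "The Investigator may also withdraw subjects who violate the study plan". Both are worded as leaving the study. Section 7.2 has no separate category for someone who stops CBT but stays in follow-up.

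The Subject Replacement paragraph, which comes next, says that those who discontinue early "will not be replaced once they have been randomized". It continues: "Every effort will be made to obtain follow-up data on all participants randomized".

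Section 8.3 sets the analysis population: "We will use an intention-to-treat approach of all randomized participants for all primary analyses". It then provides for the non-adherent separately: "Additional analyses will be conducted with protocol-compliant participants".

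Two sentences fix what each arm has to adhere to before the week-16 assessment (T2). Section 6.2.2 says "After individuals in the WL group complete their second fMRI assessment, they will be offered CBT treatment". Section 7, on the waitlist group, says "We will request that they not seek treatment for weight or binge eating disorder during the wait period". The Study Summary describes the trial as open label.

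**The concern.** The primary endpoints (Section 3.1.1) are changes in BOLD response from baseline to week 16, so a participant without a T2 scan contributes no change score. If the investigator ends study participation because a CBT participant is missing sessions, that scan may never be scheduled. Before T2 the waitlist arm has no intervention to fall short on, so this ground has no counterpart there, and the investigator applies it knowing the arm.

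Two things are at stake. One is whether the primary analysis is in practice an analysis of everyone randomized. The other is whether T2 data are lost from one arm for a reason linked to outcome. If participants who engage least with CBT also change least, losing them makes the CBT arm look better than it was.

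**Working it through.** **1. Which grounds are specific to one arm before T2?**

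- Adherence to the intervention: CBT arm only. Waitlist participants start CBT after T2 (Section 6.2.2), and the adherence items in Table 2 are sessions attended and skill builders completed.
- Study procedures and visit schedules: either arm.
- Violating the study plan: either arm. A waitlist participant who seeks outside treatment is an example; this is checked at week 8 and week 16 (Section 7).

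**2. Do the sections fit together?** Section 7.2 permits an end to study participation. Subject Replacement states an intention to follow up everyone. Section 8.3 needs that follow-up. No section says that a participant discontinued for non-adherence still attends T2 for the scan and the Eating Disorder Examination (EDE). Staff could follow Section 7.2 as written and not schedule the visit.

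**3. Does the planned model deal with it?** Section 8 states no missing-data assumption, imputation or sensitivity analysis. A mixed model can keep the baseline scan of someone without T2, but it is unbiased only if missingness is at random given the modelled data. Section 8.2.2 also adds percent reduction in binge episodes as a covariate. Without a week-16 episode count that covariate cannot be computed, and a standard fit would then drop the participant altogether.

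**4. The plan's own figure.** Inputs: 40 randomized 1:1 (Section 6.2.3), 25% drop-out (Section 6.1), effect size 0.93, 80% power, one-sided 5% (Section 8.1). Completers: 40 × 0.75 = 30, or 15 per arm if losses are even. For a two-sample t test the noncentrality is 0.93 × √(15 × 15 / 30) = 2.55 on 28 degrees of freedom. Power is 79.95%, so the stated figure reproduces. It rests on 30 completers split evenly, not on all 40.

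**5. Power if losses are uneven** (effect 0.93, one-sided 5%, 30 completers, CBT:waitlist):

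- 15:15 gives 79.9%
- 12:18 gives 78.5%
- 10:20 gives 75.7%

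Power falls little. The issue is bias.

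**6. Illustrative bias.** The documents give no number of removals for non-adherence, so *k* and *g* below are assumptions. Let *k* of 20 CBT participants be removed before T2, with a mean change *g* SD less favorable than the mean *m* of those retained. The mean of everyone assigned to CBT is [(20 − *k*)*m* + *k*(*m* − *g*)]/20 = *m* − (*k*/20)*g*. Analyzing only those retained therefore shifts the contrast by (*k*/20)*g*:

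- *k* = 2, *g* = 0.5: 0.05 SD
- *k* = 3, *g* = 0.5: 0.075 SD
- *k* = 5, *g* = 0.5: 0.125 SD
- *k* = 5, *g* = 1.0: 0.25 SD

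With no true effect, a nominal one-sided 5% t test of 20 − *k* CBT against 20 waitlist participants would reject in about 6.8%, 7.8%, 9.9% and 17.7% of trials respectively. This is an unadjusted comparison of means and leaves out the covariate in Section 8.2.2.

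**7. Extreme case.** If everyone removed would have shown zero change, an apparent effect of 0.93 corresponds to 0.93 × (20 − *k*)/20 among all assigned: 0.84 for *k* = 2 and 0.70 for *k* = 5. The overstatement is 20/(20 − *k*) − 1, or 11% to 33%.

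**The case against.** The best defense is the Subject Replacement paragraph. It opens with participants who discontinue early and says follow-up will be sought from everyone randomized. Read together, the three sections can be consistent: discontinuation is possible, data are still sought, all are analyzed, and non-adherence matters only for the protocol-compliant analysis. This has real force. A reader might infer from Section 7.2 that a discontinued participant has no T2 scan and that the intention-to-treat promise cannot be kept. The documents do not say so. What remains is that the follow-up sentence is a general commitment, and nothing tells staff how it applies to someone whose participation has been ended under Section 7.2.

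A reader might also infer that Section 7.2 can remove only CBT participants. That is true before T2 of one ground and not of the others.

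The size and direction are open too. Removal is discretionary and may be rare. Five removals would equal the whole CBT share of the planned 25% drop-out if losses were even (20 × 0.25 = 5), leaving none for voluntary drop-out, and some non-adherent participants would miss T2 whatever Section 7.2 said. Someone who remits early may also stop attending, which would push the bias the other way. The 0.93 is a detectable effect, not an expected one. These objections stand against any firm claim about size or direction, but they do not supply the missing statement about T2.

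**Conclusion.** The point holds as a cheap improvement. Section 7.2 gives an unblinded investigator discretion to end study participation for poor adherence to CBT, a ground that before T2 exists in one arm only. The follow-up and intention-to-treat commitments do not say that T2 data are still collected in that case. The all-randomized analysis is therefore not assured, and the CBT effect could be biased, plausibly upward if less engaged participants change less.

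The size cannot be determined from the documents. Under the assumptions of 2 to 5 removals out of 20 and a gap of 0.5 to 1.0 SD, the bias is about 0.05 to 0.25 SD. The 11–33% overstatement should be read only as the extreme case of zero change in everyone removed. The documents do not support saying that the effect would be overstated, or by how much. The sample-size arithmetic is not in question.

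**What to change.** Reconcile Section 7.2, the Subject Replacement paragraph and Section 8.3 with one or two sentences in Section 7.2:

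- Separate discontinuation of the intervention from withdrawal from the study.
- State that non-adherence to CBT alone does not end data collection, and that the T2 scan and EDE are still sought unless consent is withdrawn or scanning is unsafe.

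Decisions about stopping the intervention are left as they are. Non-adherent participants are left out only of the protocol-compliant analysis that Section 8.3 already plans.

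The cost is the $100 scan payment (Section 24) and scanner time for a few more T2 visits. For 2 to 5 participants the payments come to 2 × $100 = $200 up to 5 × $100 = $500. The documents give no figure for scanner time. Since those who discontinue are not replaced, each T2 assessment kept also protects the sample: with all 40 scanned at T2, the t-test power at 0.93 would be 89.3%, against 79.9% with 15 per arm.
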